4. SPECIFIC AIMS/HYPOTHESES

Our primary objective is to assess stone dusting ablation efficiency (Joules/stone volume ablated) between both laser systems *in vivo* for ureteroscopic stone treatment (Ventimiglia et al., 2021, 2023; Corrales and Traxer, 2022). Secondary objectives include assessing stone dusting ablation speed (stone volume ablated/lasing time), stone-related clinical outcomes, effect of hard stones (>1000HU) on ablation efficiency, and safety/complication profile of both laser systems.

We hypothesize that dusting ablation efficiency and speed of the p-Tm:YAG laser will be non-inferior to TFL for the treatment of renal stones totaling 7-20 mm in diameter with similar clinical and safety/complication outcomes.

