5. BACKGROUND AND SIGNIFICANCE

Ureteroscopic stone treatment is a minimally invasive procedure commonly performed for kidney stones. Recently, the thulium fiber laser (TFL) has demonstrated effectiveness in this procedure. A new laser system developed by Dornier, the Thulio pulsed Thulium:YAG (p-Tm:YAG) is beginning to be studied *in vitro* (Huusmann et al., 2021; Petzold et al., 2021a, 2021b, 2021c, 2021d; Kraft et al., 2022a, 2022c; Kwok et al., 2023) and *in vivo* (Panthier et al., 2023). Dornier Thulio p-Tm:YAG may represent an attractive new laser platform, with comparable properties to TFL including decreased retropulsion, (Petzold et al., 2021b) smaller dust, (Petzold et al., 2021a) and improved ablation efficiency relative to Ho:YAG. (Petzold et al., 2021a; Kraft et al., 2022a; Solano et al., 2023) Moreover, the p-Tm:YAG laser has been shown to be effective in treating a wide range of human stone types. (Kwok et al., 2023). The Dornier Thulio p-Tm:YAG laser has been tested clinically in a limited fashion via pilot studies in URS (Panthier et al., 2023) and the RevoLix Hybrid Thulium Laset (HTL) was studied in mini-PCNL (Bergmann et al., 2023). However, limited research has directly compared its efficacy and safety and no prospective comparative trials have been published. This study aims to investigate whether Dornier Thulio p-Tm:YAG laser is non-inferior to TFL in terms of dusting ablation efficiency (J/mm³) and dusting ablation speed (mm³/s) for ureteroscopic stone treatment.

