Perioperative fields will include total operative time, presence of preoperative alpha blockers, procedure time, laser time, setting of lithotripsy that was used most frequently during the case, total laser energy used, use of active fragment extraction (# of fragments beyond that for analysis/culture), 1st assist skill level (PGY level), use and size of ureteral access sheath, intra-operative complications, and treatment on any anticoagulation.

Postoperative fields will include length of hospitalization, postoperative complications, stone composition, need for ancillary procedures, stent duration, and stone-free status on postoperative low-dose CT imaging (axial slices 2.5mm and sagittal/coronal 3mm) using residual stone ABC grading (0 fragments, <2mm fragments, 2-4mm fragments) as recently recommended by Journal of Endourology. (Stern et al., 2023).

The trial will be a prospective, study of patients with renal stones 7-20 mm in size located at or above the level of the ureteropelvic junction. Total enrollment will be limited to 100 patients (50 ureteral and 50 renal) for the study with goal of 50 patients (25 ureteral and 25 renal) in each arm. This goal recruitment number is based on a power analysis for a noninferiority study utilizing a pre-determined non-inferiority margin of 20%, and was calculated to provide 90% power with a one-sided significance level of 0.025.

Table 1, adapted from (Solano et al., 2023), was constructed using results from recently published studies reporting ablation efficiency (J/mm³). The median ablation efficiency for TFL in the table was of 5.6 J/mm³ (Enikeev et al., 2021) with IQR 3-9.9. Assuming a normal distribution, the median and IQR values were used to estimate mean of 6.2 J/mm³ and standard deviation of 5.2 J/mm³. (Wan et al., 2014; Luo et al., 2018) Non-inferiority margin was set at 20% (6.2-1.2=5.0 J/mm³). Estimated mean difference between TFL and Tm:YAG ablation efficiencies was 0 based on a recent systematic review by an international expert in the field (Solano et al., 2023). Data was input into a validated sample size calculator <https://app.sampsize.org.uk/> as previously described. (Flight and Julious, 2016; Negida, 2020) A sample size of 24 participants per group (n=48 total) was found to provide 90% power to detect a non-inferiority margin of 20% with a one-sided significance level of 0.025.

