In a separate power calculation using data from the only published in-vitro direct comparison of TFL to Tm:YAG revealed an average ablated weights across all laser configurations to be 0.61g (SD= 0.44 g) for p-Tm:YAG and 0.76g (SD= 0.51 g) for TFL. (Kraft et al., 2022b) Using a mean difference of 0.16g and a non-inferiority margin of 20% (0.76g-0.15g=0.61g) with a population SD of 0.47g, data was input into a validated sample size calculator <https://app.sampsize.org.uk/> as previously described. (Flight and Julious, 2016; Negida, 2020) A sample size of 24 participants per group (n=48 total) was found to provide 90% power to detect a non-inferiority margin of 20% with a one-sided significance level of 0.025.

| Laser | Reference | N | Stone size (mm ³) | Stone density (HU) | Laser on time (min) | Ablation speed (mm ³ /s) | Ablation efficacy (J/mm ³) |
|------------|----------------------------|--------------------|-------------------------------|-------------------------|---------------------|-------------------------------------|--|
| TFL | (Enikeev et al., 2021) | 14 9 | 179 (94-357) | 985 ± 60 | 1.2 (0.5-2.7) | 2.33 (1.33-4.65) | 5.6 (3-9.9) |
| | (Haas et al., 2023) | 56 | 288 (77-371) | 990 (726-1203) | 5.1 (1.7-7.3) | 8.05 (4.55-11.53) | 2.4 (1.1-3.2) |
| | (Korolev et al., 2021) | 2386 (1083 - 4202) | | | | | |
| | | | 900 (625-1275) | 5.31 (3.3-9.6) | 6.8 (4.6-12.5) | 3.38 (1.68; 5.36) | |
| | | 1186 (905-2317) | 1100 (750-1350) | 5.2 (1.95-8.8) | 5.1 (3-8.7) | 4.89 (2.77-7.44) | |
| | | | 1337 (878-3665) | 1170 (636-1300) | 5.9 (3.55-10.53) | 4.4 (3.4-7.6) | 4.21 (3.3-6.12) |
| | (Sierra et al., 2022) | 346 (147-1800) | 900 (400-1500) | 17.4 (13.2-24.4) | 0.3 (0.2-1.3) | 8.7 (4.8-65.2) | |
| | | | 1125 (294-4000) | 950 (725-1125) | 26.38 (17-57.1) | 0.7 (0.4-1.2) | 14.3 (7.8-24.7) |
| | (Taratkin et al., 2022) | 15 3 | 279.6 (139.4-615.8) | 1,020 ± 382 (250-1,900) | 2.7 (1.6-6.6) | 1.7 (1.0-2.8) | 13.3 (7.3-20.9) |
| | (Vaddi et al., 2022) | 12 6 | 1061.85 ± 806.81 | 985.82 ± 302.57 | 19.78 ± 12.32 | 0.86 ± 0.31 | 14.35 ± 5.70 |
| Ho: YAG | (Haas et al., 2023) | 52 | 319 (59-521) | 1028 (808-1286) | 4.8 (1.2-6.7) | 10.46 (3.41-14.46) | 1.6 (0.7-2.2) |
| | (Ventimiglia et al., 2021) | 30 | 1599 (630-3502) | 1040 (753-1275) | - | 0.7 (0.4-0.9) | 19 (14-24) |
| | (Patil et al., 2022) | 51 | 2770.54 ± 1977.06 | 1211.68 ± 259.81 | 11.30 ± 8.23 | 4.64 ± 2.07 | 9 ± 5 |

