| | (Azilgareeva et al., 2022) | 25 | 508.9 (293.2-628.3) | 1124.0 ± 329.0 | 15.0 (11.2-18.3) | 0.6 (0.5-0.9) | 30.8 (22.8-41.2) |

The electronic data will be stored in the REDCap (Research Electronic Data Capture) application (16,17). REDCap is a stand-alone system with no interaction or connectivity to other systems, and the database is located behind the UCSD firewall. Users must have a UCSD provided ID/password to connect to REDCap and their ID must be specifically

authorized in order to access an individual study's data. All changes to the data, and each "record viewed" is logged back to the individual ID with a timestamp. When the case report forms are configured, each field has an attribute that can be set to flag it as an "identifier". This "identifier" is used by REDCap to control certain actions related to the field. REDCap also has several built-in functions to control the exporting of identifying information. Individual users are each granted specific export rights, including – None, De-Identified, and Full. Additional export de-identification options include removing identifiers and dates, hashing IDs and date shifting.

Demographic data, pre-operative, and post-operative data will be summarized using mean, median and quartiles (continuous variables) and frequency and percent (categorical variable).

Intention-to-treat analysis will be performed. Non-inferiority analysis will be conducted for the primary endpoints, with a pre-specified non-inferiority margin of 20%.

Secondary endpoints will be compared using appropriate statistical tests (e.g., t-test, chi-square test). All analyses will be performed using a statistical software package (e.g., SPSS).

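### The non-inferiority limit for the primary outcome is on the wrong side: energy per volume is better when lower, yet the limit is set below the TFL mean (5.0 J/mm³) instead of above it (7.4 J/mm³)

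*Protocol*

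**What the plan says.** Protocol section 4 defines the primary outcome as energy over volume: "Our primary objective is to assess stone dusting ablation efficiency (Joules/stone volume ablated) between both laser systems". The hypothesis takes TFL as the reference: "dusting ablation efficiency and speed of the p-Tm:YAG laser will be non-inferior to TFL". Section 5 gives the units and claims non-inferiority for two measures: "non-inferior to TFL in terms of dusting ablation efficiency (J/mm³) and dusting ablation speed (mm³/s").

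The sample-size text in section 6 derives TFL planning values from a published median and interquartile range, to "estimate mean of 6.2 J/mm³ and standard deviation of 5.2 J/mm³", and then sets the limit: "Non-inferiority margin was set at 20% (6.2-1.2=5.0 J/mm³"). A second power calculation, based on in-vitro ablated weight, uses the same form: "a non-inferiority margin of 20% (0.76g-0.15g=0.61g"). The analysis text at the end of section 6 says only: "Non-inferiority analysis will be conducted for the primary endpoints, with a pre-specified non-inferiority margin of 20"%. It names no side.

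On ablation speed, section 4 says: "Secondary objectives include assessing stone dusting ablation speed (stone volume ablated/lasing time"). The hypothesis in the same section and the aim in section 5 nevertheless claim non-inferiority for it.

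**The concern.** A non-inferiority limit marks the worst result for the new treatment that is still acceptable, so it must lie on the unfavourable side of the reference. For J/mm³ the unfavourable side is upward, because more joules per mm³ means more energy spent for the same work. A limit of 5.0 lies on the favourable side of 6.2.

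The subtraction has the same form as the ablated-weight calculation, where it is correct because more weight ablated is better. It would also suit speed in mm³/s. It does not suit J/mm³.

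The direction of the primary test is at stake. An analyst who takes the written limit at face value would use either a test that rewards a less efficient laser or one that demands a 20% advantage. If the side were changed only after the data were seen, the change would look driven by the result.

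**Working it through.** **Inputs from the protocol.** TFL mean 6.2 and SD 5.2 J/mm³; margin 20%, rounded to 1.2 (unrounded 0.20 × 6.2 = 1.24); assumed true difference 0; one-sided level 0.025; 90% power; 50 per arm planned; 1:1 allocation (section 8).

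**1. Planning values.** From the median 5.6 and quartiles 3 and 9.9 with n = 149, the cited estimation methods give a mean of 6.20 and an SD of 5.17. The 6.2 and 5.2 are reproduced.

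**2. Side of the limit.** Let D = mean(p-Tm:YAG) − mean(TFL) in J/mm³. Lower is better, so D > 0 is unfavourable.
- Limit as written: 6.2 − 1.2 = 5.0, i.e. D = −1.2, a level 1.2/6.2 ≈ 19% better than TFL.
- Limit on the unfavourable side: 6.2 + 1.2 = 7.4, i.e. D = +1.2.
- If a 20% loss is defined on the reciprocal scale (mm³/J): 6.2/0.8 = 7.75. This is also above 6.2, so the side does not depend on how the 20% is defined.

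**3. Consequence at 50 per arm.** SE = 5.2 × √(2/50) = 1.04. Probabilities are from the non-central t distribution with 98 degrees of freedom. Where two values are given, they are for margins 1.2 and 1.24.

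| True D | 5.0 as lower limit: lower bound > −margin | Correct side: upper bound < +margin |
|---|---|---|
| +1.24 (20% more energy) | 0.642, 0.656 | 0.023, 0.025 |
| +3.1 (50% more energy) | 0.984, 0.985 | 0.0001 |
| 0 (equal) | 0.207, 0.218 | 0.207, 0.218 |
| −1.24 (20% less energy) | 0.023, 0.025 | 0.642, 0.656 |

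Hand check of the first cell by normal approximation: (1.24 + 1.2)/1.04 − 1.96 = 0.386, and Φ(0.386) = 0.65.

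**4. The other literal reading.** If p-Tm:YAG must be shown to lie below 5.0 (upper bound of D below −1.2), the test becomes superiority by 20%. Equal lasers then pass about 0.1% of the time, since Φ(−1.2/1.04 − 1.96) ≈ 0.0009. A laser needing 20% less energy passes about 2.7% of the time (margin 1.2).

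**5. The protocol's sample size.** n per group = 2 × 5.2² × (1.960 + 1.282)² / margin².
- Margin 1.2: 395 per group (396 with the t distribution), not the stated 24.
- Margin 5.0: 23 by the normal formula, 24 with the t distribution (power 90.3%; 89.0% at 23).

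The stated 24 therefore appears when 5.0 is entered as the margin. What was typed into the calculator is inferred, not stated. The size of the margin is a separate problem, but the match suggests that 5.0 was carried forward as a working number. By symmetry, moving the limit to the correct side leaves n unchanged. Power at 50 per arm with margin 1.2 is about 21% on either side.

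**The case against.** The strongest defence is that 5.0 appears once, in brackets, in a power justification. The analysis statement carries only an unsigned 20%, and an analyst who knows the unit and the hypothesis can apply it on the correct side. The confidence bound and the order of subtraction are details usually left to a statistical analysis plan, which may exist. This stands to the extent that their absence is not a fault and the correct side may yet be used. It does not remove the error, because the protocol states a limit for this outcome and states it wrongly. A plan that followed it would inherit the mistake, and one that used +1.2 would contradict the protocol.

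It is also fair that the 64–66% figure belongs to one of two readings, and that the other is extremely strict, not permissive. Both are shown above, and neither gives a valid non-inferiority test.

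The sample-size match suggests that 5.0 served as a margin width and not as a test limit. That is a reason to treat the error rates as conditional, but it does not make the written limit right.

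Finally, 7.4 is one choice and 7.75 another. Only a limit above 6.2 follows from the definition; 7.4 is the version that keeps the protocol's own 1.2. The status of speed is a separate side point and adds no weight here.

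**Conclusion.** The concern holds, and the limit must be corrected before analysis. That it is on the wrong side follows directly from the definition of the outcome and needs no assumption about the data. The error rates are conditional on 5.0 being used as the test limit and on the protocol's SD of 5.2, approximately normal means and 50 evaluable patients per arm. As a lower limit, it raises the chance of accepting a laser that needs 20% more energy from about 2.5% to 64–66%, and cuts the chance of accepting one that needs 20% less from 64–66% to about 2.5%. As a target to be beaten, it leaves equal lasers about a 0.1% chance. Correcting the side changes neither the required sample size nor the power of about 21% at a true difference of zero.

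**What to change.** In the sample-size text of Protocol section 6, replace the subtraction with 6.2 + 1.2 = 7.4 J/mm³. Add the decision rule: p-Tm:YAG is non-inferior on ablation efficiency if the upper bound of the two-sided 95% confidence interval for p-Tm:YAG minus TFL lies below +1.2 J/mm³ (20% of the TFL planning mean). If the 20% is meant on another scale, state that scale and the resulting limit, which must still lie above 6.2.

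Separately, state whether the non-inferiority claim for speed is kept. If it is, test it against a limit 20% below TFL, because higher is better there. The difference tests that section 6 foresees for secondary endpoints would not support that claim.

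The cost is one or two sentences before analysis, with no extra data. The stated 24 per group still has to be reconciled with a margin of 1.2; this edit does not do that.

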8. RECRUITMENT

Ureteroscopic treatment of renal calculi is the standard of care treatment approach, and thus no treatments will be performed that are not considered standard of care.

Patients will be identified based on operating room schedule, clinic visits or hospital admission. They will be approached in person by study personnel.

Using block randomization, participants will be randomized in a 1:1 ratio to receive either p-Tm:YAG or TFL treatment. Surgeons will be blinded to the assigned laser treatment until in the operating room.

Project subjects will be chosen from the pool of patients presenting in a UCSD Urology clinic with kidney stone disease who have chosen to undergo flexible ureteroscopy with holmium laser lithotripsy. Females of childbearing age are given a pregnancy test prior to the procedure. No person shall be excluded from being offered the trial except those based on the above inclusion/exclusion criteria. Vulnerable groups such as pregnant women, fetuses; neonates; prisoners; children; groups with known cognitive impairment; or institutionalized individuals will not be involved in this project. This project has neither direct benefit to individual participants nor monetary compensation, and as such is less likely to lead to coercion of patient populations.

This project will be requesting a partial waiver of HIPAA authorization to be granted. Identifiers will be protected from improper use by having access restricted to project personnel which is limited to the PI and project coordinator. Identifiers will be destroyed 4 years after the project initiation or 2 years after data collection is complete. Project recruitment could not be possible without access to medical chart information which includes PHI. This access to PHI poses minimal risk as it is not used for reasons other than identifying potential participants. No PHI will be used as part of data collection for the project except name on the Informed Consent Form.

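### The sample size of 24 per group for 90% power does not follow from the protocol's own inputs; those inputs give about 12% power at 24 per arm and 21–22% at the planned 50

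*Protocol*

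**What the plan says.** The sample-size justification is in section 6 (Research Design and Methods) of the protocol.

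- **Outcome distribution.** From one published TFL series, "the median and IQR values were used to estimate mean of 6.2 J/mm³ and standard deviation of 5.2 J/mm³".
- **Margin.** "Non-inferiority margin was set at 20% (6.2-1.2=5.0 J/mm³".
- **Assumed truth.** "Estimated mean difference between TFL and Tm:YAG ablation efficiencies was 0".
- **Result.** "A sample size of 24 participants per group (n=48 total) was found to provide 90% power to detect a non-inferiority margin of 20"%, at a one-sided level of 0.025.
- **Planned size.** "Total enrollment will be limited to 100 patients (50 ureteral and 50 renal) for the study with goal of 50 patients" in each arm. This goal is also attributed to a power analysis with a 20% margin, which "was calculated to provide 90% power with a one-sided significance level of 0.025". Section 8 gives 1:1 allocation.
- **Second calculation, from in-vitro ablated weights.** "Using a mean difference of 0.16g and a non-inferiority margin of 20% (0.76g-0.15g=0.61g) with a population SD of 0.47g". It too arrives at 24 per group.

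The analysis paragraph at the end of section 6 applies the same 20% margin to the primary non-inferiority comparison.

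**The concern.** The SD (5.2) is more than four times the margin (1.2). With a true difference of zero, a two-arm comparison of that kind needs hundreds of patients per arm, so 24 cannot be right. In both calculations the bracket that defines the margin ends in the retained mean (5.0 J/mm³ and 0.61 g) and not in the margin (1.2 J/mm³ and 0.15 g), which points to a likely source of the error.

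The protocol tells its readers that the primary test is 90% likely to succeed if the lasers are equivalent. If that is badly wrong, the most likely outcome is a failed non-inferiority test that says little about the device, and it could be taken as evidence of inferiority.

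**Working it through.** **Inputs (protocol, section 6).** SD σ = 5.2; mean 6.2; true difference 0; margin m = 1.2 as printed, or 0.20 × 6.2 = 1.24 unrounded; one-sided alpha 0.025 (z = 1.96); power 90% (z = 1.2816); 1:1 allocation. No dropout rate is stated and none is applied.

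**Are the mean and SD the problem?** No. Applying the cited median/IQR conversions to the source row (5.6, IQR 3–9.9, n = 149) gives a mean of 6.2 and an SD of 5.17, which matches the protocol.

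**Required size.** n per arm = 2 × [σ(1.96 + 1.2816)/m]².

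| Value used as margin | Normal approximation | Exact t |
|---|---|---|
| 1.2 | 395 | 396 |
| 1.24 | 370 | 371 |
| 5.0 (retained mean) | 22.7, so 23 | 24 (power 90.3%) |

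The printed 24 is reproduced by the exact t calculation when 5.0 is entered as the margin. That would be 5.0/6.2 = 81% of the mean, not 20%. Relaxing the other settings does not rescue it: one-sided alpha 0.05, 80% power and margin 1.24 still need 218–219 per arm. For 24 per arm to give 90% power at a 20% margin, the SD would have to be about 1.3.

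**Power under the stated inputs.** Power ≈ Φ(m/[σ√(2/n)] − 1.96).

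- n = 24: standard error 5.2 × √(2/24) = 1.501. For m = 1.2, Φ(0.799 − 1.96) = 12.3%; for m = 1.24, 12.8%. Exact t: 12.0% and 12.5%.
- n = 50: standard error 5.2 × √(2/50) = 1.04. For m = 1.2, Φ(1.154 − 1.96) = 21.0%; for m = 1.24, 22.1%. Exact t: 20.7% and 21.8%.
- n = 25 (one of the two 25-patient strata per arm): exact t 12.3% and 12.8%.

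**Precision at 50 per arm.** The 95% confidence interval half-width is 1.984 × 1.04 = 2.06 J/mm³. To keep the interval inside a margin of 1.24, the observed difference must favour p-Tm:YAG by at least 2.06 − 1.24 = 0.82 J/mm³, which is 13% of 6.2. With 50 per arm, 90% power is reached only for a margin of about 3.4 J/mm³ (55% of 6.2).

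**In-vitro calculation.** SD 0.47 g, assumed deficit 0.16 g.

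- Margin 0.61 g (retained mean): distance to the margin 0.61 − 0.16 = 0.45; n = 2 × (0.47 × 3.2416/0.45)² = 22.9, so 23 (normal) and 24 (exact t). This is the same pattern and the same printed answer.
- Margin 0.15 g (as stated): distance 0.15 − 0.16 = −0.01. The assumed truth lies beyond the margin, so power is 2.1% at 24 per arm and 1.9% at 50, and it falls as n grows.
- The printed means differ by 0.76 − 0.61 = 0.15 g. Against a margin of 0.15 the assumed truth sits on the boundary and power is 2.5% at any n. Against the unrounded 0.152, power is 2.6% at 24 per arm, and 90% would need more than a million per arm.
- If the true difference were 0, 202–208 per arm would be needed.

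**The case against.** The arithmetic is not open to dispute: nothing elsewhere in the protocol corrects it, and a separate analysis plan could not make the printed sentence true. The fair objections concern scope and wording.

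- **The power figures depend on SD 5.2 and mean 6.2.** These come from a series in ureteral stones, whereas section 7 requires renal stones and excludes concomitant ureteral ones. This stands as a qualification. Other TFL rows in Table 1 give different answers at 50 per arm. For 14.35 ± 5.70 the margin is 2.87 and power about 70% (84 per arm needed). For 13.3 (7.3–20.9), taking SD = 13.6/1.35 = 10.07, the margin is 2.66 and Φ(2.66/2.015 − 1.98) is about 26%. For 2.4 (1.1–3.2), taking SD = 2.1/1.35 = 1.56, the margin is 0.48 and power about 33%. None of these reaches 90%.
- **The mechanism is inferred.** The calculator entries are not shown, the normal formula gives 23 and not 24, and a margin of 5.05 would also return 24. That stands, but two unrelated data sets both returning 24 under the same substitution is strong support. The error does not depend on its cause.
- **Direction.** Section 4 defines efficiency as energy per volume ablated, so lower is better, and a bound of 6.2 − 1.2 lies on the favourable side. This is a separate defect in the same line. It does not alter the size of the margin or the power.
- **Misreading a failed trial as inferiority is a risk, not something the protocol says it will do.** Agreed. A sentence on interpretation would remove the risk.

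**Conclusion.** The concern holds. Under the protocol's own assumptions (SD 5.2, true difference 0, margin 1.2–1.24 J/mm³, one-sided 0.025), 90% power needs 371–396 per arm, about 15 to 16 times the stated 24. Power is about 12% at 24 per arm and 21–22% at the planned 50. Two identical lasers would fail to show non-inferiority in roughly four trials out of five.

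The in-vitro calculation gives no support, because its assumed deficit is at or beyond its own margin apart from rounding. That the retained mean was entered as the margin is the likely explanation, not an established fact. The absolute power figures would shift with a different SD and mean, but no TFL row tested from the protocol's table brings 50 per arm to 90%.

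**What to change.** Rewrite the sample-size paragraphs in section 6:

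1. Use 1.2 (or 1.24) J/mm³ as the margin, and place the bound on the unfavourable side, above the TFL mean, since higher J/mm³ is worse.
2. Remove the 24-per-group result and both statements of 90% power. State that 50 per arm gives about 21–22% power under the stated assumptions, with an expected 95% confidence interval half-width of about 2.1 J/mm³. If the ureteral/renal split is kept and only 25 per arm contribute to the comparison, give 12–13%. That split has to be reconciled with the renal-only criteria in section 7.
3. Delete the in-vitro calculation.
4. State that failure to show non-inferiority will be reported as inconclusive, with the estimate and interval.

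Optionally, analyse log(J/mm³) adjusted for pre-operative stone volume and Hounsfield units, both already collected. The margin must then be restated as a ratio. The gain is uncertain: with a coefficient of variation of 5.2/6.2 the log-scale SD is √ln(1 + 0.839²) = 0.73, and a ratio margin of 1.2 gives about 23% power at 50 per arm before adjustment. Any real improvement would have to come from the covariates.

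The cost is protocol wording and a much less favourable stated power. No extra patients are needed unless the investigators wish to keep 90% power at a 20% margin.

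### The second (in-vitro) power calculation claims 90% power at 24 per group, but its own inputs put p-Tm:YAG at or beyond the non-inferiority limit and give about 2–3%

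*Protocol*

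**What the plan says.** Section 6 (Research Design and Methods) of the protocol contains two sample size calculations. The first uses ablation efficiency in J/mm³, the primary endpoint. The second is presented as separate and uses in-vitro ablated weights, reported "to be 0.61g (SD= 0.44 g) for p-Tm:YAG and 0.76g (SD= 0.51 g) for TFL". Its inputs are stated in one sentence: "Using a mean difference of 0.16g and a non-inferiority margin of 20% (0.76g-0.15g=0.61g) with a population SD of 0.47g". The result is the same as that of the first calculation: "A sample size of 24 participants per group (n=48 total) was found to provide 90% power to detect a non-inferiority margin of 20" per cent, at a one-sided significance level of 0.025. The planned enrolment is 50 per arm.

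**The concern.** In a non-inferiority calculation, power depends on the distance between the assumed true difference and the margin. Here that distance is zero or negative. The limit, 0.76 − 0.15 = 0.61 g, equals the mean assumed for the test laser, and the printed difference of 0.16 g exceeds the 0.15 g margin. A trial whose assumed truth sits on the limit has power equal to its one-sided alpha, whatever its size. A claim of 90% at 24 per group is therefore impossible on these inputs.

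What is at stake is the credibility of the sample size. A reader sees two calculations from different data that agree on 24 per group and 90% power, and will take the second as corroboration of the first. If the first were corrected and the second left alone, an unsupported 90% statement would remain in the protocol.

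**Working it through.** **Inputs (all from section 6 of the protocol)**
- Test laser, p-Tm:YAG: mean 0.61 g, SD 0.44 g.
- Control, TFL: mean 0.76 g, SD 0.51 g.
- Deficit of p-Tm:YAG: 0.16 g as printed; 0.76 − 0.61 = 0.15 g from the printed means.
- Margin: 0.15 g as printed; 20% of 0.76 g is 0.152 g.
- SD 0.47 g, one-sided alpha 0.025, power 90%. Allocation is 1:1 (section 8).

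**Formulas**
- Per-arm size (normal approximation): n = 2 × [SD × (1.96 + 1.2816) / (margin − deficit)]².
- Power: two-sample t test, non-central t with 2n − 2 degrees of freedom and non-centrality (margin − deficit) / (SD × √(2/n)). The standard error is 0.47 × √(2/24) = 0.136 g at 24 per arm and 0.47 × √(2/50) = 0.094 g at 50 per arm.

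**Attempt to reproduce 24 per group**

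With the stated inputs, margin − deficit = 0.15 − 0.16 = −0.01 g. No n exists that gives 90% power. Power at 24 per arm uses non-centrality −0.01/0.136 = −0.074.

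| Deficit (g) | Margin (g) | Margin − deficit (g) | Power, 24/arm | Power, 50/arm | n/arm for 90% |
|---|---|---|---|---|---|
| 0.16 | 0.15 | −0.010 | 2.1% | 1.9% | none |
| 0.15 | 0.15 | 0 | 2.5% | 2.5% | none |
| 0.15 | 0.152 | 0.002 | 2.6% | 2.6% | about 1.16 million |
| 0.14 | 0.152 | 0.012 | 3.1% | 3.3% | about 32,000 |

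The last row is the most favourable reading of rounding: the printed means could hide a deficit between 0.755 − 0.615 = 0.14 g and 0.765 − 0.605 = 0.16 g. Its size is 2 × (0.47 × 3.2415 / 0.012)² ≈ 32,237 per arm. Varying the SD from 0.44 to 0.51 g keeps power at 24 per arm between 2.1% and 2.6% for the first three rows.

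**Other readings of the difference, margin 0.15 g**
- True difference of zero: power 19% at 24 per arm and 35% at 50 per arm; 90% needs 208 per arm.
- Sign reversed, p-Tm:YAG better by 0.16 g: distance 0.15 + 0.16 = 0.31 g; power 61% at 24 per arm and 90% at 50 per arm.

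Neither gives 24 per group.

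**What does give 24**

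For 90% power, 24 per arm needs a distance of about 0.44 g. Using the limit 0.61 g in place of the margin, with difference 0.16 g, gives 0.61 − 0.16 = 0.45 g. Power is then 90.1% at 24 per arm and 88.8% at 23, so n = 24.

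The first calculation behaves in the same way. It states "Non-inferiority margin was set at 20% (6.2-1.2=5.0" J/mm³, with SD 5.2 and difference 0. Using 5.0 as the margin gives 90.3% at 24 per arm and 89.0% at 23, so again n = 24. Using the stated margin of 1.2 gives 12% at 24 per arm and 21% at 50 per arm, and 90% needs 396 per arm.

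**The case against.** The arithmetic is hard to contest; the case on the other side is about weight and wording.

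- *It is a second instance of one root error.* If the limit was entered for the margin in both calculations, the first is the important one because it concerns the primary endpoint. This is fair, and the two should be corrected together. It does not make the second statement correct.
- *The outcome is not measured in the trial.* Ablated weight in grams is not an endpoint, the data are in vitro and averaged over laser configurations, and planned enrolment is 50 per arm rather than 24. All true. Correcting this calculation alone changes no endpoint, margin or analysis.
- *Whether the assumed truth is at or beyond the limit depends on rounding.* With the unrounded margin of 0.152 g and the printed means, the assumed truth is 0.002 g inside the limit. This is correct but moves power only from 2.5% to 2.6%.
- *The 32,000 figure combines inputs that do not quite fit.* A deficit of 0.14 g implies a TFL mean of 0.755 g, 20% of which is 0.151 g; the distance is then 0.011 g and the size about 38,000 per arm. The 32,000 should be read only as a lower bound.
- *The mechanism is inferred.* The calculator entries are not shown. A reversed sign gives 49 per group by the normal approximation and 50 by the t test, close to the stated total of 48. That reading contradicts the printed means, does not give 24 per group, and cannot explain the first calculation, where the difference is zero. The limit-for-margin explanation fits both, but remains an inference, and the finding does not depend on it.

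**Conclusion.** The concern holds. On its own inputs the second calculation has power of about 2–3%, not 90%, at 24 per group and equally at the planned 50 per arm. Across the rounding of the printed figures the range is 1.9% to 3.3%, and 90% power is either unreachable or needs more than 30,000 per arm.

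This rests on a two-sample comparison of means with a common SD of 0.47 g, one-sided alpha 0.025, and the direction of the printed means (p-Tm:YAG lower than TFL). The consequence is limited to the sample size justification, because ablated weight is not a trial endpoint. The calculation gives no support to the first one; taken at face value, its means would predict that non-inferiority is almost never shown.

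**What to change.** Delete the in-vitro calculation as support for 24 per group and 90% power. This is the cleaner course, since the trial does not measure ablated weight.

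If the sponsor prefers to keep it, the text should reconcile the 0.16 g difference with the printed means of 0.76 and 0.61 g. It should also say that under these in-vitro means p-Tm:YAG lies at or beyond the non-inferiority limit, so that power on that outcome would be about 2–3% at the planned size, and label this as an in-vitro illustration, not the power of the trial.

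The first calculation should be checked at the same time for the same substitution of limit for margin.

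For the in-vitro calculation, the cost is a change of protocol wording. The price is the loss of one supporting argument for the sample size.
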